11.4 Planned recruitment rate

To reach the target sample size of 76 randomised participants, and assuming recruitment rate of 50%, 152 potential participants will need to be approached during the 78 weeks of recruitment, or just under 2 potential participants per week.

The recruitment base will be five NHS London memory services, with 600 MCI patients per year (four times the screening target). Camden & Islington Memory Services alone exceed 1200 new patient referrals per year, of which 20% have MCI (or 240 people per year). We estimate that based on these five patient identification centres, the referral rate will be approximately six potential participants per week; two participants will be suitable and will agree to participate (one per research assistant). We conducted a small (n=12) feasibility study with similar but less restrictive inclusion and exclusion criteria as the proposed trial. This study recruited seven participants in four weeks, of which five had been confirmed to have untreated hearing loss and would have met inclusion criteria for the planned trial (1.25 potential participant per week), based on a single memory service, so the projected figures should be achievable.

11.5 Randomisation methods

Individual-level randomisation with randomly varying block sizes to ensure equal number of participants allocated to each intervention arm.

11.6 Statistical analysis

11.6.1 Summary of baseline data and flow of participants

List of variables to be used to assess baseline comparability of the randomised groups using means (SD) and counts (proportions) as appropriate:

- Age
- Sex
- Cognition scale: Addenbrooke Cognitive Examination (ACE-III) score
- Quality of life: SF36, EQ-5D
- Function: 4-item Lawton-Brody IADL
- Social activities: SFDEM, UCLA loneliness
- Frailty: grip strength
- Physical activity: as measured by accelerometry at baseline
- Geriatric Depression Score
- Self-reported hearing disability - Hearing Handicap Inventory for the Elderly – Screening version (HHIE-S)
- Phoneme Recognition in Quiet score (baseline)
- Hearing Threshold PTA average (0.5-4 KHz)

We will produce a consort flow diagram (<http://www.consort-statement.org/>) to illustrate the flow of participants in the trial, based on draft (presented as Fig 3).

11.6.2 Primary outcome analysis

We will produce estimates and 95% Confidence Intervals for:

- Recruitment: Number of participants who will be randomised into the trial, divided by the total number of screened participants, expressed as percentage
- Retention: Number of participants that do not drop out before 6 month endpoint assessment, divided by the total number of randomised participants, expressed as percentage
- Acceptability of the Hearing Intervention: proportion of participants allocated to the Hearing Intervention completing ≥ 2 intervention sessions, divided by the total number of participants randomised to the Hearing Intervention.

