6.1 Eligibility criteria

6.1.1 Inclusion criteria for TACT

Inclusion (all to be satisfied)

1. Clinical diagnosis of MCI following internationally recognised clinical criteria (ICD 10), as diagnosed (or confirmed) by an NHS memory Service and not superseded by a diagnosis of dementia.
2. **55 years of age or older** (as MCI under 55 is rarely linked to neurodegeneration and future dementia)
3. **Living in the community** (not in hospital or residential care).
4. **Mental capacity to provide informed consent to trial procedures.**
5. **Audiometric hearing impairment.** Participants must have adult-onset hearing impairment with a four-frequency pure tone average (0.5, 1, 2, 4 kHz) in the better-hearing ear of ≥ 25 decibels Hearing Level (dB HL) and < 70 dB HL or a pure tone audiometric threshold at 4 KHz in the better ear of ≥ 30 decibels dB HL.
6. **Phoneme Recognition in Quiet score $\geq 60\%$ in better ear.** A phoneme recognition in quiet score $< 60\%$ suggests hearing impairment that may be too severe to benefit from conventional amplification devices such as hearing aids.
7. No previous prescription of hearing aids, or, if the potential participant has been prescribed hearing aid in the past, they report no hearing aid use at all in the past month (see temporary exclusion criteria number 8a under temporary exclusion criteria), or low use because of lack of perceived efficacy. Low use is defined as less than 2 hours per day on average over the past 7 days (when at home and in usual health).
8. **Willingness to participate, be randomized and adhere to the protocol.** Participants must be willing and able, in the opinion of the researchers, to consent to participate in the trial, to be randomized, and to adhere to the trial protocol, including willingness to wear hearing aids on a daily or near daily basis if allocated to the intervention arm, and to be followed for the duration of the trial (30 weeks).

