11.1 Primary Outcome

This pilot trial aims at establishing the feasibility of a full-size trial of the hearing aid intervention versus healthy ageing intervention in people with MCI. This future trial will be a scaled-up version of the present pilot, modified with any lessons learnt in the current trial. The pilot's primary objective is therefore to establish feasibility of recruitment, randomisation, retention, and the acceptability of the trial interventions as follows:

1. Recruitment and randomisation: Proportion of eligible participants who are randomised into the trial – expected value $\geq 50\%$.
2. Retention: proportion of participants who are followed for the 6 months of trial duration, and endpoint measures are obtained – expected value $\geq 80\%$.
3. Acceptability of the Hearing Intervention: proportion of participants allocated to the Hearing Intervention completing ≥ 2 intervention sessions – expected value $\geq 80\%$ of intervention group.

The Primary Outcome of the Remote Hearing Intervention sub-study (during COVID-19), in keeping with the overall TACT primary objective, will be the feasibility of the RHI, in terms of:

1. Recruitment: achieving $n=12$ participants
2. Acceptability of the RHI proportion of participants allocated to the Hearing Intervention completing $\geq 2/3$ intervention sessions – expected value $\geq 80\%$.
3. Retention: proportion of participants completing outcome collection – expected value $\geq 80\%$.

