11.3 Sample size calculation

This pilot trial will assess the feasibility of proceeding to the future definitive RCT of sufficient duration to detect differences in cognitive changes between arms. The main feasibility questions that the pilot aims to answer are: (a) is the trial feasible, in the sense of resulting in sufficiently high recruitment, randomisation and sufficiently low dropout at 6 months; (b) is the Hearing Intervention deliverable and acceptable to participants; (c) estimate the difference in hearing aid use at 6 months between the Hearing Intervention and Healthy Ageing Intervention arms to inform sample size estimates for the future trial. We are including cognitive outcomes to assess their feasibility and acceptability, and to provide estimates including standard deviation to be used in the sample size calculation for the full trial. As a feasibility study, the current trial is not powered to detect differences in the cognitive outcomes between the arms. Therefore, only descriptive analyses will be performed using the data collected. No formal power calculation is necessary, and instead the sample size has been determined as to provide sufficient precision (sufficiently narrow confidence intervals) for trial estimates of recruitment and randomisation, dropout, acceptability of the intervention, and difference in hearing aid usage between arms, as detailed below.

With 76 randomised participants, we will achieve the following 95% confidence intervals (CI) for our expected estimates of recruitment, randomisation, dropout, acceptability of the intervention, and difference in hearing aid adherence between the Hearing Intervention and Healthy Ageing Intervention at the end of trial [88]:

1. Recruitment and randomisation of eligible participants with a MCI diagnosis from NHS community memory clinics. Target: 50% of eligible participants will be randomised; with n=76 recruited subjects the 95% CI would be [39-61].
2. Follow-up: target of 80% randomised participants with complete follow-up at 6 months,

95%CI with n=76 would be [71-89].

3. Acceptability of the Hearing Intervention: proportion of participants allocated to the Hearing Intervention completing ≥ 2 intervention sessions – expected value $\geq 80\%$ of intervention group, 95% CI with n=76 would be [71-89].

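### Recruitment is targeted as randomised/eligible but analysed as randomised/screened, and retention is targeted on endpoint data but analysed as not dropping out, so neither analysis matches its progression limit

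*Protocol*

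**What the plan says.** **Recruitment.**
- Protocol 11.1 defines the first primary outcome as "Proportion of eligible participants who are randomised into the trial", with an expected value of at least 50%.
- Protocol 11.3 repeats that base and attaches the interval: "Target: 50% of eligible participants will be randomised; with n=76 recruited subjects the 95% CI would be [39-61".
- Protocol 11.6.2, the analysis of the same outcome, has "Number of participants who will be randomised into the trial, divided by the total number of screened participants, expressed as percentage".
- Protocol 11.4 (planning, not an outcome definition) applies 50% to a further base: "assuming recruitment rate of 50%, 152 potential participants will need to be approached".
- Protocol 6.1.1, inclusion criterion 8, is headed "Willingness to participate, be randomized and adhere to the protocol". Exclusion criterion 6 in 6.1.2 removes the unwilling.
- Protocol 8.1 orders the screening visit as consent, then non-audiological eligibility including willingness, then hearing tests, then randomisation of those who meet every criterion.

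**Retention.**
- Protocol 11.1 has "proportion of participants who are followed for the 6 months of trial duration, and endpoint measures are obtained", expected to be at least 80%. Section 11.3 also speaks of complete follow-up.
- Protocol 11.6.2 counts "Number of participants that do not drop out before 6 month endpoint assessment", over all randomised.

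**Use.** The end of 11.3 reads these estimates against their intervals: inside is a go signal, up to 10% below the lower limit calls for considering modifications, and lower still is a signal not to progress. There is one set of limits per outcome.

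**The concern.** Two of the three primary outcomes have an analysis that differs from the definition on which their target was set. Hearing eligibility is established at the screening visit, so the number screened exceeds the number eligible whenever anyone fails audiometry. A limit derived for randomised/eligible is then applied to a smaller ratio.

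The 11.1 denominator has its own difficulty. If a person must be willing to be randomised in order to be eligible, and randomisation follows at the same visit, almost everyone classed as eligible is randomised. A 50% target on that ratio says little about uptake.

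For retention, the 11.6.2 wording does not ask for the data that 11.1 asks for. At stake is whether the Trial Steering Committee can tell which side of a limit the pilot fell. Section 2 already states that the data on 36 participants confirm recruitment and retention, without saying under which definition.

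**Working it through.** **1. The plan's own intervals.** Formula: p ± 1.96 × √(p(1 − p)/n), with p and n from 11.3.
- Recruitment, p = 0.50, n = 76: 0.50 ± 1.96 × √(0.25/76) = 38.8% to 61.2%. The protocol's 39-61 is reproduced.
- Retention, p = 0.80, n = 76: 0.80 ± 1.96 × √(0.16/76) = 71.0% to 89.0%. The protocol's 71-89 is reproduced.

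The go limits are therefore 39% and 71%. I read 10% below as percentage points (an assumption), which puts the modify floors at 29% and 61%. A relative reading gives 0.9 × 39 = 35.1% and 0.9 × 71 = 63.9%.

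**2. Recruitment, eligible against screened.** Let u be the share of eligible people who are randomised and E the share of screened people who are eligible. If refusers are counted among the screened, randomised/screened = u × E. The protocol gives no value for E, so I show a range at the target u = 50%:

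| E | randomised/eligible | randomised/screened | Reading under 11.6.2 |
|---|---|---|---|
| 100% | 50% | 50.0% | go |
| 80% | 50% | 40.0% | go |
| 5/7 = 71% (feasibility study, 11.4) | 50% | 35.7% | modify |
| 50% | 50% | 25.0% | below the 29% floor |

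The reading leaves go when E < 0.39/0.50 = 78%, and falls below the modify floor when E < 0.29/0.50 = 58%.

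**3. Recruitment, literal reading of eligible.** With willingness built in, u is close to 1, so randomised/eligible is near 100% and randomised/screened is about E. With E at 12/17 = 71% (share with untreated hearing loss in the preparatory work, 7.1), both ratios are above 39% and neither reads modify. Steps 2 and 3 are alternatives: they use different meanings of *eligible* and cannot both hold.

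**4. Retention.** At the planned n = 76:
- 54/76 = 71.1%, go.
- 53/76 = 69.7%, modify (under either reading of 10%).

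So if 54 have not dropped out and one of them lacks endpoint measures, 11.6.2 reads go and 11.1 reads modify. Away from the boundary it takes more: 58 not dropped out is 58/76 = 76.3%, and five of them without endpoint measures brings it to 53/76.

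**5. The figure in 11.4.** 76/0.50 = 152. With 50% defined on eligible people, 152 is a count of eligible people, and the number to approach is 152 divided by their eligible share. Purely as an assumption, take 12/17 as that share. Its 95% Wilson interval is 46.9% to 86.7%, so the number is 152/0.867 = 175 to 152/0.469 = 324. Untreated hearing loss is only part of eligibility, so even this range is only indicative.

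**The case against.** The best case against acting strongly has four parts.

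- **The limits are guidance.** The Trial Steering Committee decides on all outcomes and lessons learnt. Section 11.6.3 and the CONSORT diagram will show numbers referred, consented, screened and randomised, so other yields stay visible. This stands, and it limits the damage.
- **The recruitment switch is not established.** A reader might infer that the protocol's own data push recruitment to about 35%, into the modify band. They do not. That figure needs half of the consented, tested and eligible people to decline, whereas consent and willingness come before audiometry in 8.1, so refusers mostly leave earlier. It also rests on small samples measuring untreated hearing loss, not full eligibility. This stands.
- **Approached is not a third outcome definition.** Section 11.4 is planning text. Its expectation of two joining out of six referred (33%) is a share of referrals, which no outcome uses as a denominator, so it cannot be set against 39%. Nor do the documents support one replacement for 152. This stands.
- **Dropout is used loosely.** Section 2 equates low dropout with retention, and 11.3 announces dropout but lists complete follow-up. The protocol does not define dropout as formal withdrawal, so a reader should not infer that every missed 6-month visit would be counted as retained. This stands only in part: 11.6.2 as worded still omits the endpoint measures that 11.1 requires.

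Two other defences fail. The version history mentions a change to the recruitment definition, but both definitions are in the current body. The protocol leaves hearing-aid-use measurement to the SAP, but it fixes recruitment and retention itself, each in two ways.

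**Conclusion.** The concern holds as a contradiction between the outcome definitions and their analysis, and that much needs no assumption: eligible (11.1, 11.3) against screened (11.6.2), and endpoint measures obtained (11.1) against not dropped out (11.6.2). In both cases the progression limits were set on one definition and the analysis uses the other. The literal meaning of *eligible* also makes the recruitment target weak, because it absorbs willingness.

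The size is conditional. For recruitment, the reading changes from go to modify only if 50% of eligible people are randomised, refusers are counted among the screened, and under about 78% of the screened are eligible; the documents establish none of these. For retention, one participant is enough at the boundary with 76 randomised, provided that someone can remain in the trial without endpoint data. The documents do not show that either reading will in fact change.

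**What to change.** 1. **11.6.2, recruitment.** Use the 11.1/11.3 denominator, eligible participants.
2. **Define eligible once.** Leave out the willingness criteria (inclusion 8 and unwillingness in exclusion 6), and apply the rest as far as eligibility was assessed. Count people so assessed who decline as eligible but not randomised. Report separately how many refuse before audiometry. Their hearing eligibility is unknown, so they cannot be placed in the denominator, and the ratio should be read beside that count because it may otherwise stay high.
3. **Other yields.** Report randomised/screened and randomised/approached descriptively, without the 39-61 limits.
4. **11.6.2, retention.** Number with 6-month endpoint measures obtained, divided by all randomised.
5. **11.4.** State that 152 is the number of eligible people implied by 50% uptake, and that the number to approach is larger and depends on the eligible share. Label any figure, such as 175 to 324, as an assumption.

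The cost is wording in the protocol, carried into the SAP, which 11.6.3 says will be written before database lock. The added burden is to record at what point, and after which assessments, each person declined. The downside is that reported recruitment and retention may look less favourable.

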 - (a) Potential participants will be excluded if hearing aids were prescribed in the past three months, irrespective of their use; however, we will contact these potential participants again after 3 months following prescription of their hearing aids and they will be eligible if they report no or low use of hearing aids. Low use is defined as less than 2 hours per day on average over the past 7 days (when at home and in usual health).
 - (b) Participants determined to have occluding cerumen as per otoscopy. These participants may be enrolled after cerumen removal. We will advise participants with occluding cerumen to access accredited cerumen removal services, following recent NICE guidelines (<https://cks.nice.org.uk/earwax>, and "Hearing loss in adults: assessment and management"; NICE Guideline, June 2018 [NG98]). Participants who are identified as needing cerumen removal will be advised to consult their GP to arrange cerumen removal. They will also be offered reimbursement if they choose to have privately arranged cerumen removal by an accredited provider instead. If practicable, and at the discretion of the trial audiologist, participants may also be offered cerumen removal by the trial audiologist, who has undergone necessary training for cerumen removal procedures.

6.1.3 Eligibility criteria for participants for the Remote Hearing Intervention sub-study (COVID-19)

1. For the single-arm Remote Hearing Intervention sub-study during COVID-19 pandemic, we will invite those participants that had been consented for the randomised trial prior to the onset of COVID-19, therefore meeting the inclusion and exclusion criteria at the time they consented to participate in TACT, and who either
 - (a) completed the healthy ageing intervention and are not using hearing aids; or
 - (b) were included in the trial but not could not complete their allocated intervention due to the onset of COVID-19.
2. Potential participants will be excluded if in the opinion of the research team, would be unable to complete remote procedures.
3. Potential participants will be excluded if they report any new ear pain or discharge or any audiological symptoms that would require face to face audiological assessment prior to inclusion.

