4. Difference in daily hearing aid adherence between arms: target of 50% difference between the Hearing Intervention and Healthy Ageing Intervention arms in the proportions of participants maintaining hearing aid use at 6 months (end of follow-up), 95% CI with n=76 would be [31-69].

Mean, proportions, differences in means and proportions with corresponding 95% confidence intervals will be calculated as appropriate for the cognitive scales and other trial outcomes, to inform the sample size calculation for a full scale trial.

Criteria for the decision of progression to the main trial

We judge that these confidence intervals provide acceptable ranges to inform continuation to the main trial. The final decision to “go” or “stop”, that is, whether to proceed or not to the main trial, will be taken by the Trial Steering Committee after the end of trial and with consideration of whether the trial has met its primary and secondary outcomes, as well as any lessons learnt during the pilot.

As a **guidance to this decision**, we anticipate that if the 4 endpoint estimates above in this section, as measured in the pilot trial, fall within their respective expected confidence intervals as detailed above, this will be a “go” signal for a full scale trial. If the endpoint estimates fall up to 10% below the lower limit of their target confidence interval (as detailed above in this section) we will consider whether modifications to the trial design to improve these endpoints would be sufficient to remediate these issues when proceeding to the main trail. If any of these endpoints fall below these minimal rates this will be a “do not progress to RCT” signal.

The Remote Hearing Intervention sub-study (COVID-19) will contribute to this decision by providing initial descriptive data and a qualitative assessment on the feasibility and acceptability of a remote version of the Hearing Intervention.

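### The protocol's statements on retention disagree about participants halted by COVID-19, and under the Section 11.1 definition the halt itself lowers retention towards the stop limit

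*Protocol*

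**What the plan says.** The protocol describes retention in several places.

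- **Section 11.1, item 2:** "proportion of participants who are followed for the 6 months of trial duration, and endpoint measures are obtained", expected to be at least 80%. Section 11.3 sets its target in similar terms, as complete follow-up at 6 months.
- **Section 11.6.2:** "Number of participants that do not drop out before 6 month endpoint assessment, divided by the total number of randomised participants". Dropping out is not defined.
- **Section 2 (Summary):** before COVID-19, 36 participants were randomised with complete data, and this is said to confirm recruitment and retention. The total number randomised is not given.

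Section 6.1.3 (also the Summary and Section 6.3) acknowledges people who were included in the trial but "could not complete their allocated intervention due to the onset of COVID-19". Their number is not given. Section 3 calls the home-based intervention unsuitable during the pandemic, and the Summary says a remote version will be piloted instead. The remote sub-study collects a shortened battery about 4 weeks after the hearing aids arrive (Section 8.4). The TACT endpoint visit is at 6 months, with a 4-week tolerance.

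Section 11.3 sets the progression guidance. An estimate inside its target interval is a go signal; for retention the interval is 71 to 89%. The next band is "If the endpoint estimates fall up to 10% below the lower limit of their target confidence interval", where design changes are considered. Beyond that, "If any of these endpoints fall below these minimal rates this will be a “do not progress to RCT” signal".

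**The concern.** Retention in a pilot is meant to show whether people will stay in a full trial. A participant whose visits the trial itself suspended gives no information on that. Under Section 11.1 this person has no 6-month endpoint and counts as not retained, like someone who walked away. Under the wording of 11.6.2 the same person may count as retained, because being stopped is arguably not dropping out, although no endpoint exists. If the Summary's statement is read as an analysis of completers, the person is not counted at all.

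Sections 11.1 and 11.3 carry text for the remote sub-study, but the TACT definition of retention and its limits make no provision for halted participants. The figure sent to the Trial Steering Committee therefore depends on which section is followed. If it is Section 11.1, the estimate is biased downwards by an event that says nothing about willingness to stay.

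**Working it through.** **Reproducing the limit.** For 80% with n=76, 0.80 ± 1.96 × √(0.80 × 0.20 / 76) gives 71.0 to 89.0%, which matches Section 11.3. The go limit is 71%. The minimal rate is 71 − 10 = 61% if the 10% means percentage points, or 71 × 0.9 = 63.9% if it is relative.

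**Retention under Section 11.1 with all randomised as denominator.** Let m be the number halted with no 6-month endpoint (not stated). Two cases are shown: no ordinary dropout, 36/(36+m); and ordinary dropout at the planned 20%, so that 36 completers come from 45 people, 36/(45+m).

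| m | No ordinary dropout | 20% ordinary dropout |
|---|---|---|
| 0 | 100% | 80.0% |
| 5 | 87.8% | 72.0% |
| 6 | 85.7% | 70.6% |
| 10 | 78.3% | 65.5% |
| 12 | 75.0% | 63.2% |
| 15 | 70.6% | 60.0% |
| 21 | 63.2% | 54.5% |
| 24 | 60.0% | 52.2% |

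- With no ordinary dropout, retention falls below 71% from m=15 (m=14 gives 36/50 = 72.0%), below 63.9% from m=21 (m=20 gives 36/56 = 64.3%) and below 61% from m=24 (m=23 gives 36/59 = 61.02%).
- With 20% ordinary dropout the same limits are crossed at m=6, m=12 and m=15.

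**How large m could be.** Section 11.4 plans 76 randomised in 78 weeks, or 0.97 per week. Session D falls at week 9-10 (Section 8.3).

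- People still in the intervention phase, the group that Section 6.1.3 acknowledges: 0.97 × 10 ≈ 10, so 36/46 = 78%. With the 14-day visit tolerance, 0.97 × 12 ≈ 12, so 36/48 = 75%. Both are go signals if there was no ordinary dropout.
- Everyone within 26 weeks of randomisation, if all of them lost the 6-month visit: 0.97 × 26 ≈ 25.3, so 36/61.3 = 58.7%. At other assumed accrual rates: 0.5 per week gives 73.5%, 0.75 gives 64.9% and 1.25 gives 52.6%.

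**Acceptability, for comparison.** The criterion is at least two sessions, "divided by the total number of participants randomised to the Hearing Intervention". Session B is at week 5-6, so only Hearing-arm participants halted before it count against the criterion. Assume 18 of the 36 are in that arm and all had two sessions. With 5 to 10 weeks to the second session and 0.97 to 1.25 randomised per week:

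- Lowest loss: 0.97 × 5/2 = 2.4 people of 18 + 25.3/2 = 30.7, giving 92%.
- Highest loss: 1.25 × 10/2 = 6.25 people of 18 + 32.5/2 = 34.25, giving 82%.

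A stop signal would need 11 halted before Session B (18/29 = 62.1%, below 63.9%) or 12 (18/30 = 60.0%, below 61%).

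**The case against.** The strongest reply has four parts.

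1. **The formula in 11.6.2 may already spare these people.** On its plain wording, a suspended participant has not dropped out. That is a fair reading. It conflicts with Section 11.1, though, and counts as retained people with no endpoint.
2. **The number is unknown, and the acknowledged group is small.** About 10 people at planned accrual leaves retention at 78% if nobody else was lost. This stands as a limit on the size of the effect. No section says how many people were past Session D and awaiting the 6-month visit, or that their visits were lost. The ban on face-to-face visits in Section 3.1 is written for the remote sub-study.
3. **The limits are guidance.** The Trial Steering Committee decides and takes lessons learnt into account, so it would probably recognise the halt. This softens the consequence, but the committee would still be handed a biased or ambiguous estimate.
4. **The SAP can settle it, and all-randomised is a conventional denominator.** A detailed SAP is promised before database lock, and a flow diagram with numbers randomised and completing is already planned. But the definition, the denominator and the limits are all stated in the protocol and do not agree, so this goes beyond detail left for later. The all-randomised figure should be kept as a sensitivity analysis. Changing the denominator after 36 results are in hand in an open-label pilot has a post hoc cost, which has to be declared.

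**Conclusion.** The point holds for retention. The definitions in 11.1 and 11.6.2 and the claim in the Summary disagree on participants halted by the pandemic. Under 11.1 with all randomised as denominator, the halt alone lowers the estimate. It costs the go signal from 15 halted participants with no ordinary dropout, or from 6 with the planned 20%. The minimal rate is crossed from 21 or 24 halted in the first case, and from 12 or 15 in the second, according to whether 10% is relative or in points. These figures rest on 36 complete participants and on values of m that the protocol does not supply.

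A reader might infer three stronger things that the documents do not support:

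- **That the pilot's retention is about 59% and signals a stop.** That needs steady planned accrual up to the halt, no ordinary dropout, and loss of the 6-month visit by everyone in follow-up. None of these is stated.
- **That acceptability is distorted in the same way.** A halted participant with two sessions already counts as a success, and the estimate stays at about 82 to 92% under the assumptions above.
- **That crossing a limit ends the programme.** Section 11.3 leaves the decision to the Trial Steering Committee.

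**What to change.** - Use one definition of retention in 11.1, 11.3 and 11.6.2: the 6-month endpoint was obtained.
- Take as denominator the randomised participants whose 6-month window, including the 4-week tolerance, had closed before home visits stopped. Select them by calendar date, not by completion. Restricting to the 36 completers would give 36/36 = 100% by construction. Some of the 36 may fall outside the date rule if they were seen early in their window; they then leave both numerator and denominator.
- Apply the progression limits to this estimate, and report the all-randomised figure as a sensitivity analysis.
- Show participants halted by the pandemic separately in the flow diagram.
- State that the change was made after the halt, and fix it before database lock.
- Reword the Summary so that it does not present the 36 completers as a retention result.
- For acceptability, align the denominator in the same way, using the Session B window; little change is expected.

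The cost is wording, one extra analysis and some precision. With 45 people in the denominator, for example, the interval around 80% becomes 0.80 ± 1.96 × √(0.16/45), or 68.3 to 91.7%, against 71.0 to 89.0% with 76.
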